5.5 Withdrawal of Subjects and Discontinuation of Study

AbbVie may terminate this study prematurely at any time, either in its entirety or partially (discontinue one or more treatment groups), or at any site. The study may be discontinued or terminated in case of an unacceptable risk, any relevant toxicity, or a negative change in the risk/benefit assessment. This might include the occurrence of AEs with a character, severity or frequency that is new in comparison to the existing risk profile. In addition, data derived from other clinical trials or toxicological studies which negatively influence the benefit-risk assessment might cause discontinuation or termination of the study. The investigator may also stop the study at his/her site if he/she has safety concerns. If AbbVie terminates the study for safety reasons, AbbVie will promptly notify the investigator. Advance notice is not required by either party if the study is stopped due to safety concerns.

A subject may voluntarily withdraw from the study at any time for any reason. An investigator may discontinue a subject's participation at any time for any reason. The AbbVie Therapeutic Medical Director may mandate individual subject discontinuation from study drug in case of a safety concern.

Subjects must have study drug discontinued immediately if any of the following occur:

- Abnormal laboratory result or AE that meets the criteria for discontinuation of study drug as stated in Section 6.2, or rule out safe continuation of the study drug as determined by the investigator or the AbbVie Therapeutic Area Medical Director.
- Serious infections (e.g., sepsis) that cannot be adequately controlled within 2 weeks by anti-infective treatment or would put the subject at risk with continuation of the study drug.
- Subject is non-compliant with TB prophylaxis (if applicable) or develops active TB at any time during the study.
- Malignancy, except for localized NMSC or carcinoma in-situ of the cervix.
- The subject develops anaphylactic reactions or anaphylactic shock.
- The investigator believes it is in the best interest of the subject.

- The subject requests withdrawal from study drug or the study.
- Eligibility criteria violation was noted after the subject started study drug and continuation of the study drug would place the subject at risk.
- Introduction of prohibited medications or dosages and continuation of the study drug would place the subject at risk.

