6.2 Toxicity Management

The management of specific AEs and laboratory parameters are presented in Table 3. For subjects who discontinue study drug but continue study participation and are on standard of care therapies, these toxicity management requirements do not apply (including alerts from the central laboratory) and any intolerability to standard of care therapies should be managed by the prescribing physician.

Elective surgery will not be allowed during the first 24-weeks of study participation. If the subject undergoes elective surgery, study drug should be interrupted at least 2 weeks prior to the planned surgery. If the subject must undergo emergency surgery, the study drug should be interrupted at the time of the surgery. After surgery, allow reintroduction of study drug once the physician has examined the surgical site and determined that it has healed and there is no sign of infection.

Management of Hypersensitivity and Serious Allergic Reactions

Subjects should be closely monitored and assessed for the development of signs and symptoms of hypersensitivity reactions, including anaphylaxis. For any hypersensitivity reaction, appropriate therapy should be instituted per standard of care. Study drug should be discontinued if a subject develops anaphylaxis.

In the event of a suspected systemic post-dose hypersensitivity reaction, if the clinical situation allows, every effort should be made to obtain a serum sample within 2 hours but no later than 6 hours from

symptom onset for additional blood tests specified in the Operations Manual, Section 3.15 Hypersensitivity Testing.

Management of Serious Infections

Subjects should be closely monitored for the development of signs and symptoms of infection during and after treatment with study drug. Study drug should be interrupted if a subject develops a serious infection or a serious opportunistic infection. A subject who develops a new infection during treatment with study drug should undergo prompt diagnostic testing appropriate for an immunocompromised subject. As appropriate, antimicrobial therapy should be initiated, and the subject should be closely monitored. Study drug may be restarted once the infection has been successfully treated. Subjects who develop active TB must be permanently discontinued from study drug.

Management of Malignancy

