For any given laboratory abnormality, the investigator should assess the subject, apply the standard of care for medical evaluation and treatment following any local guidelines. Specific toxicity management guidelines for selected abnormal laboratory values are described in [Table 3](#), and may require a supplemental eCRF to be completed (Section [6.1](#)). For subjects with ongoing laboratory abnormalities that require data entry into an eCRF, an additional eCRF related to subsequent laboratory abnormalities is only required if the subject has relevant changes in history (e.g., new onset signs or symptoms) or laboratory values that have returned to normal reference range or its Baseline value followed by subsequent laboratory abnormalities meeting toxicity guidelines (considered a new event). All abnormal laboratory tests that are considered clinically significant by the investigator will be followed to a satisfactory resolution. If a repeat test is required per the Operations Manual ([Appendix G](#)) Section 3.15, the repeat testing must occur as soon as possible.

Table 3. Specific Toxicity Management Guidelines for Abnormal Laboratory Values

Laboratory Parameter	Toxicity Management Guideline
Absolute neutrophil count	
If confirmed < 1000/μL by repeat testing with new sample, interrupt study drug dosing until ANC value returns to normal reference range or its BL value.
 
Discontinue study drug if confirmed < 500/μL by repeat testing with new sample.

Absolute lymphocyte counts	
If confirmed < 500/μL by repeat testing with new sample, interrupt study drug dosing until ALC returns to normal reference range or its BL value.

Platelet count	
If confirmed < 50,000/μL by repeat testing with new sample, interrupt study drug dosing until platelet count returns to normal reference range or its BL value.

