AST or ALT	
Interrupt study drug if confirmed ALT or AST > 3 \times ULN by repeat testing with new sample and either a total bilirubin > 2 \times ULN or an international normalized ratio (INR) > 1.5.
 
A separate blood sample for INR testing will be needed to measure INR at the time of repeat testing for ALT or AST. A repeat test of INR is not needed for determination if above toxicity management criteria are met.
 
 • Interrupt study drug if confirmed ALT or AST > 3 \times ULN by repeat testing with new sample along with new appearance of fatigue, nausea, vomiting, right upper quadrant pain or tenderness, fever, rash, and/or eosinophilia (> 5% increase from Baseline). • Interrupt study drug if confirmed ALT or AST > 5 \times ULN by repeat testing with new sample for more than 2 weeks. • If ALT or AST > 8 \times ULN, interrupt study drug immediately, confirm by repeat testing with a new sample, and contact the TA MD. 
Subjects with HBc Ab+ (irrespective of HBs Ab status) or Hbs Ab+ (without a history of vaccination) and negative HBV DNA PCR testing at Screening who develop the following laboratory findings should have HBV DNA PCR testing performed within one week (based on initial elevated value):
 
 • ALT > 5 \times ULN OR • ALT or AST > 3 \times ULN if an alternative cause is not readily identified. 
 • Note: A separate blood sample for HBV DNA PCR testing will be needed at the time of repeat testing for ALT or AST. 
A positive result for HBV DNA PCR testing will require immediate interruption of study drug (unless not acceptable by local practices) and a hepatologist consultation should occur within 1 week for recommendation regarding subsequent treatment.
 
Subjects who meet any of the above criteria should be evaluated for an alternative etiology of the ALT or AST elevation and managed as medically appropriate. If applicable, the alternative etiology should be documented in the eCRF. If ALT or AST values return to the normal reference range or its Baseline value, study drug may be restarted. If restarting study drug, documentation should include reason that rechallenge is expected to be safe. If after clinically appropriate evaluation, no alternative etiology for ALT or AST elevation is found or the ALT or AST elevation has not resolved or is not trending down toward normal, the subject should be discontinued from study drug.
 
For any confirmed ALT or AST elevations > 3 ULN, complete the appropriate supplemental hepatic eCRF(s).

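### The ALT/AST restart sentence in Table 3 is wider than the stop sentence beside it: it permits restart after a resolved elevation even when no cause was found

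*Protocol*

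**What the plan says.** Protocol Section 6.2, Table 3, AST or ALT row, sets several criteria for interrupting study drug and asks that any subject meeting one be evaluated for another explanation of the elevation. Three sentences then govern what follows.

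- Restart: "If ALT or AST values return to the normal reference range or its Baseline value, study drug may be restarted".
- Condition on restart: "If restarting study drug, documentation should include reason that rechallenge is expected to be safe".
- Stop: the triggers, judged once the work-up is complete, are "no alternative etiology for ALT or AST elevation is found or the ALT or AST elevation has not resolved", with failure to fall towards normal as a further trigger. The instruction is that "the subject should be discontinued from study drug".

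Protocol Section 5.5 opens its list of compulsory stops with "Subjects must have study drug discontinued immediately if any of the following occur". The first item is "Abnormal laboratory result or AE that meets the criteria for discontinuation of study drug as stated in Section 6.2". The item goes on to cover results that, in the judgement of the investigator or the sponsor's medical director, rule out safe continuation. Section 5.5 does not mention the restart permission in Table 3.

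**The concern.** The restart sentence looks only at the laboratory value. The stop sentence looks at the cause as well, and because its triggers are joined by *or*, failure to find a cause is enough by itself. The permission therefore extends to subjects whom the stop sentence would take off drug.

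The rule decides whether someone is re-exposed after a possible drug-related liver injury. One way into it is ALT or AST above 3 x ULN with bilirubin above 2 x ULN, the pattern that SAP Section 10.3 lists as a possible Hy's Law case. Protocol Section 4.2 describes this as the first study of the drug in RA subjects. The synopsis plans about 270 sites, and the Activity Schedule has dosing to Week 180. Consistent handling across that many sites depends on the written rule.

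**Working it through.** The documents state no figure for this rule, so there is none to reproduce. The check is to list every case and see which sentences apply.

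**Inputs.** Cause: found or not found. Course: resolved (back to normal or Baseline), trending down but not resolved, or neither. That gives 2 x 3 = 6 cases.

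**Rules, taken literally from Table 3.**

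- Restart applies if resolved.
- Stop, reading A: no cause found, or not resolved, or not trending down.
- Stop, reading B: no cause found, or neither resolved nor trending down.

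Two readings are needed because the last clause of the stop sentence can be parsed either way.

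| Course | Cause | Restart permitted | Stop (A) | Stop (B) | Both apply | Restart permitted after fix |
|---|---|---|---|---|---|---|
| Resolved | Found | Yes | No | No | No | Yes |
| Resolved | Not found | Yes | Yes | Yes | **Yes** | No |
| Trending down | Found | No | Yes | No | No | No |
| Trending down | Not found | No | Yes | Yes | No | No |
| Neither | Found | No | Yes | Yes | No | No |
| Neither | Not found | No | Yes | Yes | No | No |

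**Result.** Restart and stop overlap in 1 of 6 cases under reading A and in 1 of 6 under reading B. It is the same case each time: resolved, no cause found. The finding does not depend on how the last clause is parsed. Once restart also requires an identified cause, the overlap is 0 under both readings, and no stop instruction is lost because the stop sentence is untouched.

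**Does other text settle the overlapping case?**

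- The restart sentence is a permission (*may*), the stop sentence a direction (*should*), and Section 5.5 an obligation (*must*). All three can be obeyed by stopping, so the weight of the wording is towards stopping.
- Section 5.5 is framed around an abnormal laboratory result. Once the value is back to normal or Baseline, a site could argue that the item no longer describes the subject.
- The rechallenge sentence asks for a written reason that restarting is expected to be safe. It does not say that the reason must be an identified cause, so it can be read as inviting case-by-case justification.
- Neither section contains an *unless* or *provided that* linking the restart and stop sentences.

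**The case against.** The strongest reply is that the documents already give the answer. A general permission is ordinarily limited by a more specific direction, and here the specific direction concerns subjects with no alternative cause. Section 5.5 points the same way with stronger language. A site that discontinues is always compliant. This largely stands. A reader might infer that the protocol contradicts itself outright, leaving sites equally entitled to restart or to stop. The documents do not support that, because *may* set against *should* and *must* favours stopping. What remains is that this ranking has to be inferred, and that the reference to an abnormal result leaves a gap for a value that has normalised.

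A second reply concerns timing. The stop sentence operates after evaluation. If evaluation ends without a cause while values are still raised, the stop direction comes first and the restart condition has not yet been met. The overlap is then mainly among subjects whose values normalise before, or as, evaluation closes. This narrows the group but does not empty it.

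A third reply is that safeguards exist, and they do:

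- A restart needs a documented safety reason, which is hard to write when no cause is known.
- Table 3 requires supplemental hepatic eCRFs for any confirmed ALT or AST above 3 x ULN, and Section 6.1 requires one when drug is interrupted or discontinued for a hepatic-related AE.
- Section 5.5 lets the sponsor's medical director mandate discontinuation.
- Section 2.2 describes an unblinded DMC and blinded team review of safety data.

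These lower the chance that an unsafe rechallenge goes unnoticed. None of them says that the stop sentence limits the restart sentence.

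**Conclusion.** The concern holds as a minor patient-safety correction. The restart sentence should not reach a case that the stop sentence covers, and it does so in exactly one: elevation resolved, no cause found. The combined text leans towards stopping, so the risk is that a site relies on the restart sentence alone.

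The affected group is expected to be small, and the documents give no rate from which to estimate it. A reader might also infer a hepatic signal, a between-arm bias or an effect on the ACR50 result. Nothing in the documents supports any of these, and no statistical quantity changes.

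The conclusion assumes that the *or* in the stop sentence is meant literally. It also rests on the protocol and SAP alone. The Operations Manual is not among the documents reviewed, so a restart-approval step there cannot be ruled out.

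**What to change.** In the AST or ALT row of Table 3, add a condition straight after the opening *If* of the restart sentence: *an alternative etiology has been identified and documented and*. The rest of that sentence stays as it is. Leave the rechallenge-documentation sentence, the discontinuation sentence and Section 5.5 unchanged.

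This brings the permission into line with the stop sentence and with the mandatory stop in Section 5.5. The cost is one clause, plus a few forgone restarts among subjects whose elevation resolved without explanation.

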7 STATISTICAL METHODS & DETERMINATION OF SAMPLE SIZE

7.1 Statistical and Analytical Plans

The statistical methods provided in this protocol will be focused on primary and secondary analyses. Complete and specific details of the statistical analysis will be described in the Statistical Analysis Plan (SAP).

The primary analysis will be conducted after all ongoing subjects have completed Week 12. This will be the only and final analysis for the Double-Blind, Placebo-Controlled Period. After the primary analysis, additional analyses may be conducted to further inform the design of a Phase 3 program. A final analysis will be conducted after all subjects have either withdrawn from the study or completed LTE Period 2 plus the safety follow-up visit. To maintain integrity of the trial, the study sites and subjects will remain blinded until all subjects have either completed the last visit of LTE Period 1 or have withdrawn from the study.

7.2 Definition for Analysis Populations

The following populations will be used for analyses:

- Intent-to-treat Population includes all subjects who were randomized and received at least 1 dose of study drug. The ITT Population will be used for all efficacy analyses.
- Safety Population in the Placebo-Controlled Period (Safety_PC) includes all subjects randomized and received at least 1 dose of study drug. This population will be used for the safety analysis in the Placebo-Controlled Period.
- All ABBV-154 Treated Population (ALL_154) includes all subjects who received at least 1 dose of ABBV-154 during the study. This population will be used to provide a comprehensive summary of safety.

7.3 Handling Potential Intercurrent Events for the Primary and Secondary Endpoints

No intercurrent events will be considered for the primary and secondary endpoints.

7.4 Statistical Analyses for Efficacy

For the Placebo-Controlled Period, subjects will be analyzed according to the treatment group randomized. All statistical tests will be performed at a 2-sided significance level of 0.1. A 95% confidence interval of the treatment difference between each ABBV-154 dose and placebo will be provided.

- For categorical variables, a pairwise, comparison will be made between each ABBV-154 dose and placebo using the Cochran-Mantel-Haenszel (CMH) test, adjusting for the actual values of stratification factors. Non-Responder Imputation incorporating multiple imputation to handle COVID-19 (NRI-MI) will be the primary approach to handle missing data for categorical endpoints.
- For continuous variables, the comparison will be made between each ABBV-154 dose and placebo based on the MMRM adjusting for treatment, visit, interaction between treatment and visit, actual values of stratification factors as fixed factors, and BL value as a covariate. The MMRM will be the primary approach to handle missing values for continuous endpoints.

Through the Placebo-Controlled and Long-Term Extension Periods, descriptive statistics by treatment sequences will be provided at each visit. Categorical endpoints will be summarized by the number and proportion of subjects who achieved the endpoint, as well as the 95% confidence interval. Continuous endpoints will be summarized by descriptive statistics including mean, standard deviation, standard error, and the 95% confidence interval of the mean. In addition, continuous endpoints through Week 24 will be summarized using estimates from the MMRM by treatment sequence, visit, interaction between treatment sequence and visit, actual values of stratification as fixed factors and baseline values as a covariate.

Summary and Analysis of the Primary Endpoint

The primary endpoint is the achievement of ACR50 at Week 12. It will be evaluated using the ITT Population based on treatment as randomized. Comparison of the primary endpoint will be made between each ABBV-154 dose and placebo using the CMH test adjusting for the actual values of stratification factors. NRI-MI will be the primary approach to handle missing values. Analysis details for NRI-MI and other sensitivity analyses (if applicable) will be provided in the SAP.

One supplementary analysis for primary endpoints is to test a pre-specified set of dose-response models among ABBV-154 dose groups and the placebo group at Week 12 using the Multiple Comparison Procedure – Modeling approach (MCP-Mod). Details of this method will be provided in the SAP.

Summary and Analysis of Secondary Endpoints

Analysis of secondary efficacy endpoints will be conducted on the ITT Population based on treatment as randomized.

Summary and Analysis of Additional Efficacy Endpoints

Additional endpoints, as described in Section 3.3, will also be analyzed.

Subgroup Analysis for Efficacy

To evaluate the consistency of efficacy across demographic and other Baseline characteristics, the following subgroup analysis will be performed on the primary endpoint:

- Baseline glucocorticoid use (yes/no)
- Number of prior failed b/tsDMARDs (1; 2 or more)
- Prior use of failed anti-TNF (yes/no)
- Prior use of adalimumab (yes/no)
- Age (\leq median/ $>$ median)
- Sex (female/male)
- Race (white/non-white)

7.5 Statistical Analyses for Safety

All safety analyses will be performed based on the Safety Population, as defined in Section 7.1. Subjects will be analyzed based on the actual treatment received. Treatment-emergent adverse events (TEAEs), laboratory assessments, and vital signs will be summarized. Key safety variables will also be summarized on the ALL_154 Population.

A TEAE for the Safety Population is defined as an AE newly occurred or worsened after the first dose of study drug and within 70 days after the last dose of study drug. The number and percentage of subjects experiencing TEAEs will be tabulated using the MedDRA system organ class and Preferred Term, by severity, and by relationship to the study drug as assessed by the investigator. Summaries (including percentages and events per 100 patient years) of SAEs, deaths, and AEs leading to discontinuation will be provided as well. Pre-treatment AEs will be summarized separately.

For selected laboratory parameters, a listing of all subjects with any laboratory value \geq Grade 3 of the Common Toxicity Criteria will be provided. Mean change in laboratory and vital signs variables will be summarized. Additional details for the safety analysis are provided in the SAP.

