3 OBJECTIVES AND ENDPOINTS

3.1 Objectives, Hypotheses, and Estimands

Primary Objective

The primary objective is to assess the safety, tolerability, and efficacy of ABBV-154 vs. placebo on background MTX for the treatment of subjects with moderately to severely active RA who have had an inadequate response to at least one prior b/tsDMARD.

The primary efficacy objective of the study is to demonstrate a higher rate of ACR50 after 12 weeks of treatment with ABBV-154 when compared to placebo in the Intent-to-Treat (ITT) Population (further described in Section 7.2), which consists of all randomized subjects who have received at least one dose of study drug. The hypothesis corresponding to the primary efficacy objective and endpoint is the proportion of subjects achieving ACR50 with ABBV-154 is greater than that with placebo at Week 12. The estimand for the primary endpoint is defined as the difference in the proportion of subjects that achieve ACR50 at Week 12, in each of the ABBV-154 dose groups compared with the placebo group in the ITT Population.

The secondary efficacy objectives of the study are to demonstrate higher efficacy of treatment with ABBV-154 when compared to placebo with respect to the secondary endpoints specified in Section 3.3; in the ITT Population. The estimands corresponding to the secondary efficacy objectives are:

- For each of the categorical secondary endpoints, the estimands corresponding to the secondary efficacy objectives are defined as follows: Difference in the proportion of subjects achieving the endpoint, in each of the ABBV-154 groups in comparison with the placebo group in the ITT Population.
- For each of the continuous secondary endpoints, the estimands corresponding to the secondary efficacy objectives are defined as follows: Difference in the mean change from baseline of the endpoint, in each of the ABBV-154 dose groups in comparison with the placebo group in the ITT Population.

Secondary Objective

The secondary objective is to assess the pharmacokinetics (PK), pharmacodynamics, and immunogenicity of ABBV-154.

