3.5 Safety Measures

1. Treatment-emergent adverse events, serious adverse events (SAEs), and AEs leading to discontinuation of the study drug;
2. Occurrence of potentially glucocorticoid related AEs; and
3. Potentially clinically significant laboratory, vital signs, and electrocardiogram (ECG) variables.

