10.2.1 Treatment-Emergent Adverse Events

Treatment-emergent AEs are defined as any AE with the onset that is after the first dose of study drug and with an onset date no more than 5 half-lives of the study drug (i.e., 70 days). Events where the onset date is the same as the study drug start date are assumed to be treatment-emergent, unless the study drug start time and the AE start time are collected and the AE start time is prior to the study drug start time. All treatment-emergent AEs will be summarized overall, as well as by primary MedDRA SOC and Preferred Term. The SOCs will be presented in alphabetical order, and the PTs will be presented in alphabetical order within each SOC.

The number and percentage of subjects experiencing treatment-emergent AEs will be summarized.

In the ALL_154 population, treatment-emergent AEs are defined based on the first dose of ABBV-154.

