10.2.2 Adverse Event Overview

An overview of AEs will be presented consisting of the number and percentage of subjects experiencing at least one event for each of the following AE categories:

- Any treatment-emergent AE
- Any treatment-emergent AE related to study drug according to the investigator
- Any severe (CTCAE grade ≥ 3) treatment-emergent AE
- Any serious treatment-emergent AE
- Any treatment-emergent AE leading to discontinuation of study drug
- Any treatment-emergent AE leading to death
- Adverse Events of Special Interest (formally known as Safety Topics of Interest)
- All deaths
 - Deaths occurring ≤ 70 days after last dose of study drug
 - Deaths occurring > 70 days after last dose of study drug.

The overview of AEs per 100 patient-years of exposure will also be provided for the above categories.

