10.2.4 Treatment-Emergent Adverse Events per Patient-Years of Exposure

Exposure-adjusted AEs per 100 patient-years will be provided, where AEs per 100 patient-years of exposure are defined as the number of AEs divided by the total exposure in 100 patient-years. The study drug exposure is defined as the last dose date plus $5 \times$ half-life (70 days), minus the first dose date.

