10.3 Analysis of Laboratory Data

Data collected from central and local laboratories, including additional laboratory testing due to an SAE, will be used in all analyses, except for Baseline where SAE-related laboratory assessments on or before the first dose of study drug will be excluded. The clinical laboratory tests defined in the protocol operations manual (e.g., hematology and clinical chemistry) will be summarized.

Each laboratory variable will be summarized for all time points (starting with Baseline) with the number of non-missing observations, mean and standard deviation, median, minimum and maximum. Mean change from baseline to each applicable post-baseline visit will be summarized for selected laboratory variables, with the number of observations, baseline mean, and visit mean. The change from baseline mean, standard error, and 95% confidence interval will be presented for the mean change from baseline within each treatment group and difference between treatment groups (ABBV-154 vs. placebo) as applicable. This summary and change from baseline summary will be presented once by treatment sequence.

Changes in laboratory parameters will be tabulated using shift tables either by NCI CTC criteria or other criteria listed in Appendix B. A shift table from baseline either to the worse value (based on NCI CTC criteria) during treatment or to minimum and maximum value (based on normal range), will be created. A similar shift table will be provided to summarize shifts from baseline to the final post-baseline value.

Laboratory abnormalities meeting CTC criteria grade 3 and 4 will be summarized.

Laboratory abnormalities will be evaluated based on Potentially Clinically Important (PCI) criteria (based on NCI CTC criteria, except for those listed in Appendix B). For each laboratory PCI criterion, the number and percentage of subjects who have a laboratory value meeting the criteria will be summarized. Listings will be provided to summarize subject-level laboratory data for subjects meeting PCI criteria. In the evaluation of PCI laboratory values, the baseline value for the ALL_154 population will

be determined by the last non-missing measurement recorded on or before the date of the first dose of study drug in the corresponding ABBV-154 treatment group (which may be different than the first dose of study drug received in the study).

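### Safety versus placebo is part of the primary objective, but adverse events are reported per arm with no difference from placebo and no confidence interval

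*Protocol*

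**What the plan says.** Protocol 3.1 states: "The primary objective is to assess the safety, tolerability, and efficacy of ABBV-154 vs. placebo on background MTX". Protocol 3.5 lists the safety measures. Treatment-emergent AEs, SAEs and AEs leading to discontinuation come first, and the second item is "Occurrence of potentially glucocorticoid related AEs". An adjudication committee will review systemic glucocorticoid AEs (Protocol 5.10, SAP 12.1).

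The planned AE analyses are these:

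- Protocol 7.5: "The number and percentage of subjects experiencing TEAEs will be tabulated using the MedDRA system organ class and Preferred Term". For the graver events: "Summaries (including percentages and events per 100 patient years) of SAEs, deaths, and AEs leading to discontinuation will be provided as well".
- SAP 10.2.1: "The number and percentage of subjects experiencing treatment-emergent AEs will be summarized".
- SAP 10.2.2: "An overview of AEs will be presented consisting of the number and percentage of subjects experiencing at least one event", with rates per 100 patient-years for the same categories.
- SAP 10.2.4: "Exposure-adjusted AEs per 100 patient-years will be provided".
- SAP 10.2.5 and 10.2.6: tables by system organ class and preferred term, event rates and listings for SAEs, AEs leading to discontinuation and AEs of special interest.

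For mean changes in selected laboratory variables, SAP 10.3 plans a 95% interval "within each treatment group and difference between treatment groups (ABBV-154 vs. placebo) as applicable". SAP 10.4 does the same for vital signs.

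**The concern.** An objective framed against placebo calls for an estimate against placebo. For AEs the plan stops at one column per arm, plus a total active column (SAP 10.1). It does not say how large an excess over placebo the data support, or how large an excess they exclude.

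Two features of this trial give that weight. The compound carries a glucocorticoid receptor agonist, so systemic glucocorticoid events are the obvious thing to look for. SAP section 10 nevertheless gives them no analysis of their own; they can appear only through the special-interest tables. Also, every placebo subject who continues is re-randomised to active drug at Week 12 (Protocol 5.8), so the Placebo-Controlled Period is the only one with a concurrent control. With about 85 subjects per arm, a reader could take equal small counts as reassurance, or a moderate imbalance as a signal, when neither reading is secure.

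**Working it through.** **The passages compared.**

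| Data | Difference from placebo | Interval |
|---|---|---|
| Efficacy endpoints (Protocol 7.4) | yes, each dose | 95% |
| Laboratory mean change (SAP 10.3) | yes, where applicable | 95% |
| Vital-sign mean change (SAP 10.4) | yes, where applicable | 95% |
| AEs, SAEs, discontinuations, AEs of special interest (Protocol 7.5, SAP 10.2) | none | none |

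So the sponsor does not confine itself to per-arm description of safety in general. Only the event data lack a comparison.

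**The plan's own figure.** No precision statement is made for safety. The only computed figure is efficacy power (Protocol 7.10): 13% against 13 + 22 = 35%, 85 per arm, two-sided 0.1. The pooled proportion is 0.24.

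- SE under the null = √(2 × 0.24 × 0.76 / 85) = 0.0655
- SE under the alternative = √((0.13 × 0.87 + 0.35 × 0.65) / 85) = 0.0633
- Power = Φ((0.22 − 1.645 × 0.0655) / 0.0633) = Φ(1.77) = 96.2%

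This agrees with the stated minimum of 90%. It says nothing about AE precision.

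**Precision for AEs at 85 per arm.** The documents give no AE rates, so the counts below are assumptions. The Newcombe interval for a risk difference d = p₁ − p₂ uses the Wilson limits (l, u) of each arm:

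- lower = d − √((p₁ − l₁)² + (u₂ − p₂)²)
- upper = d + √((u₁ − p₁)² + (p₂ − l₂)²)

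*3 vs 3 events.* Each arm is 3.53% (Wilson 1.21 to 9.87). d = 0 and the half-width is √(2.32² + 6.34²) = 6.8. Result: 0 (−6.8 to +6.8 points).

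*10 vs 4 events.* The arms are 11.76% (6.52 to 20.32) and 4.71% (1.85 to 11.48). d = 7.06.

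- Lower: 7.06 − √(5.25² + 6.78²) = −1.5
- Upper: 7.06 + √(8.55² + 2.86²) = +16.1

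*8 vs 2 events.* The arms are 9.41% (4.85 to 17.49) and 2.35% (0.65 to 8.18). d = 7.06.

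- Lower: 7.06 − √(4.57² + 5.83²) = −0.3
- Upper: 7.06 + √(8.08² + 1.71²) = +15.3

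*0 of 85.* The upper exact two-sided 95% (Clopper-Pearson) limit is 1 − 0.025^(1/85) = 4.2%.

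Equal counts of 3 therefore leave room for an excess of up to 6.8 points over a placebo rate of 3.5%. A count more than twice that on placebo (10 vs 4) is still compatible with no excess.

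**The case against.** **Descriptive AE tables are usual in Phase 2b, and this study does not control multiplicity (Protocol 7.9).** That is true, and such tables are not an error. But the efficacy comparisons are equally unadjusted and still carry intervals, so the lack of multiplicity control is not a reason to omit them here.

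**No information is lost.** Counts and denominators will be reported, so a reader can compute an unstratified interval from the published tables. This stands, and it limits the point to an improvement in reporting. A reader could not recover a stratified interval from those tables alone, and categories chosen after unblinding would not be pre-specified.

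**A product-level safety analysis plan may add comparisons.** SAP 10.2.6 cites it for the list of special-interest events and their search criteria, and SAP 10.4 for some vital-sign criteria. It is not among the documents. Nothing it is cited for would supply a difference or interval.

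**Stronger readings that do not hold.**

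- *That no safety variable is compared with placebo.* Laboratory and vital-sign mean changes are, and these bear on blood glucose and blood pressure.
- *That a dose-trend test is clearly needed because it is more powerful.* This depends on the assumed shape. In simulation (85 per arm, scores 0, 40, 150, 340, two-sided 0.05), assumed risks of 3/4/7/12% give 73% for trend against 62% for 340 mg eow versus placebo. With the same end points and the SAP's own EMax shape (ED50 = 83.9) it reverses to 57% against 62%. With an early plateau (3/10/12/12%) it is 38% against 62%.
- *That the glucocorticoid taper causes withdrawal events in every arm and so biases raw comparisons.* Protocol 5.4 requires the taper and asks for monitoring of adrenal insufficiency, but no passage quantifies such events. Baseline glucocorticoid use is also a randomisation stratum, so a crude difference is not biased by it.
- *That a placebo difference would test the compound's premise.* The premise (Protocol 2.1) concerns side effects from systemic glucocorticoid exposure, and there is no glucocorticoid comparator arm. A placebo difference shows excess risk only.

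**Conclusion.** The point holds for adverse events and only for them. Safety versus placebo is one of three parts of the primary objective. The event data that bear on it most directly, including glucocorticoid-related AEs, receive no difference from placebo and no interval, while laboratory and vital-sign mean changes receive both.

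The size is a matter of precision left unstated. At 85 per arm, a single dose-versus-placebo interval runs from about 7 points either side of zero at 3 events per arm to −1.5 to +16.1 points at 10 against 4. These figures rest on assumed counts and full arms of 85. They are unstratified Newcombe intervals, so those from the method proposed below will differ somewhat.

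This is a worthwhile, inexpensive improvement to a conventional plan. It does not undermine the trial, and the documents do not support extending it to a trend test.

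**What to change.** In SAP 10.2.2, 10.2.5 and 10.2.6, with a matching sentence in Protocol 7.5, add the following for Safety_PC:

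- **Estimate:** the risk difference of each ABBV-154 dose versus placebo with a 95% Miettinen-Nurminen interval. Stratify by baseline glucocorticoid use where counts allow; otherwise leave it unstratified.
- **Categories, named in advance:** any TEAE, severe TEAE, SAE, AE leading to discontinuation, and adjudicated systemic glucocorticoid AEs pooled.
- **Window:** events before the first Week 12 (LTE) dose, with an equivalent cut-off stated for subjects who never take one. TEAEs otherwise run to 70 days after the last dose, by which time placebo subjects may be on active drug.
- **Label:** descriptive and unadjusted for multiplicity.

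The cost is SAP wording and one additional table of 4 doses × 5 categories = 20 intervals; no new data are collected. The downside is that 20 unadjusted intervals can be over-read. The label and the short fixed list are meant to limit that. Rare topics such as active TB or malignancy can stay as counts and listings.
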